8.3.5 ADVERSE EVENT REPORTING

In consultation with the PIs, a trained member of the study team will submit annual reports to the IRB that will contain: 1) The number of adverse events and an explanation of how each event was handled, 2) The number of complaints (reflecting participant disposition) and how each complaint was handled; 3) The number of participant withdrawals and an explanation of why the participant withdrew or was withdrawn; and 4) The number of protocol deviations/violations and how each was handled.

In addition, the study team will submit annual reports to the DSMB summarizing the AEs.

8.3.6 SERIOUS ADVERSE EVENT REPORTING

Any study related death will be reported to the IRB and NIDCR within 24 hours of the study team's knowledge of it. Any other study related SAE will be reported to the IRB and NIDCR within 5 business days of the study team being made aware of it. The written report will be prepared in consultation with the PI. In the event that a participant either withdraws from the study or the investigator decides to discontinue a participant due to study-related SAE, the participant will be monitored by the investigator via on going status assessment until 1) a resolution is reached i.e., the problem requiring hospitalization has resolved or stabilized with no further changes expected 2) the SAE is determined to be clearly unrelated to the study intervention, or 3) the SAE results in death. Outcome of SAEs will be periodically reported to NIDCR. A summary of the SAEs that occurred during the previous year will be included in the annual progress report to NIDCR.

8.3.7 REPORTING EVENTS TO PARTICIPANTS

N/A

8.3.8 EVENTS OF SPECIAL INTEREST

N/A

8.3.9 REPORTING OF PREGNANCY

N/A

8.4 UNANTICIPATED PROBLEMS

8.4.1 DEFINITION OF UNANTICIPATED PROBLEMS

This protocol uses the definition of Unanticipated Problems as defined by the Office for Human Research Protections (OHRP). OHRP considers unanticipated problems involving risks to participants or others to include, in general, any incident, experience, or outcome that meets all of the following criteria:

- Unexpected in terms of nature, severity, or frequency given (a) the research procedures that are described in the protocol-related documents, such as the Institutional Review Board (IRB)-approved research protocol and informed consent document; and (b) the characteristics of the participant population being studied;
- Related or possibly related to participation in the research ("possibly related" means there is a reasonable possibility that the incident, experience, or outcome may have been caused by the procedures involved in the research); and
- Suggests that the research places participants or others at a greater risk of harm (including physical, psychological, economic, or social harm) than was previously known or recognized.

8.4.2 UNANTICIPATED PROBLEMS REPORTING

The investigator will report unanticipated problems (UPs) to the reviewing Institutional Review Board (IRB), the DSMB and NIDCR. The UP report will include the following information:

- Protocol identifying information: protocol title and number, PI's name, and the IRB project number
- A detailed description of the event, incident, experience, or outcome
- An explanation of the basis for determining that the event, incident, experience, or outcome represents an UP
- A description of any changes to the protocol or other corrective actions that have been taken or are proposed in response to the UP

To satisfy the requirement for prompt reporting, UPs will be reported using the following timeline:

- UPs that are serious adverse events (SAEs) will be reported to the IRB and NIDCR within 48 hours of the investigator becoming aware of the event
- Any other UPs will be reported to the IRB and NIDCR within 7 days of the investigator becoming aware of the problem
- UPS will be annually reported to the DSMB.

8.4.3 REPORTING UNANTICIPATED PROBLEMS TO PARTICIPANTS

Since UPs by definition suggest that the research places participants or others at a greater risk of harm (including physical, psychological, economic, or social harm) than was previously known or recognized, all participants who are still active in the protocol (i.e. have not completed in-person 6 month study visit) will be notified in writing of UPs and will be reconsented at the time of their next study visit.

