| Schedule Visit 1 | X | | | | | | | |
| Obtain written informed consent | | X | | | | | | |
| Care Partner Questionnaire | | X | | | X | | | X |
| Study Participant Questionnaire | | X | | | X | | | X |
| Oral Health Evaluation | | X | | | X | | | X |
| ADCS-ADL | | X | | | | | | |
| Oral Hygiene Skill Assessment Sheet | | X | | | X | | | X |
| Coaching Module | | | | | | | | |
| Tailored Oral Hygiene Instruction | | | | | | | | |

| Control Group | Screening | Time 1 (Home Visit 1) Week 1: (within 42 days) | Time 2 Week 4: (± 7 Days) | Time 3 Week 8: (± 7 Days) | Time 4 (Home Visit 2) Week 12: (± 14 Days) | Time 5 Week 16: (± 7 Days) | Time 6 Week 20: (± 7 Days) | Time 7 (Home Visit 3) Week 24: (± 14 Days) |
|---|-----------|---|---------------------------------|---------------------------------|---|----------------------------------|----------------------------------|---|
| Montreal Cognitive Assessment (MoCA) | | X | | | X | | | X |
| Educational booklet provided | | X | | | | | | |
| Detailed explanation of education booklet | | | | | | | | X |
| Electronic Toothbrush Data Download | | | | | | | | |
| Post Intervention Interview— participant | | | | | | | | |
| Post Intervention Interview—Care partner | | | | | | | | |
| Distribution of a smart electronic toothbrush | | | | | | | | X |
| Exit Interview w/participant | | | | | | | | X |
| Exit Interview w/care partner | | | | | | | | X (via phone) |

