2.3 RISK/BENEFIT ASSESSMENT

2.3.1 KNOWN POTENTIAL RISKS

Oral health evaluation: The clinical oral evaluations involve some manipulation of the gingiva, which may cause mild discomfort and bleeding. No periodontal probing will be performed during the oral health evaluation, and thus risk to participants is minimal.

Breach of Confidentiality: There is a small risk that unauthorized persons could get access to personal or study-related participant information.

Questionnaires and Cognitive Screening: Individuals may feel self-conscious about their cognitive weaknesses when completing the cognitive screening instrument. However, they will have completed similar tests before since they currently have a diagnosis of mild dementia; thus, it is expected that this familiarity will attenuate any discomfort. In addition, our study coordinators will be trained specifically to address the individual's concerns and to provide appropriate reassurances. The other questionnaires may seem somewhat tedious, but there is no other negative risk related to completing the measures.

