Participants in Treatment Group 1 and Treatment Group 2 will receive two smart electronic toothbrushes that collect the time, date and duration of brushing (each toothbrush stores approximately 15 days of the brushing data). The study coordinator will download the toothbrush data on a monthly basis to allow sufficient memory storage space for subsequent data collection. Participants in Treatment Group 2 will be asked to self-report oral hygiene behavior using a calendar log throughout the study. They will also receive individualized instruction on oral hygiene technique, cueing strategy development, oral hygiene monitoring, and coaching four times over the course of the first 3 months of the study. One module is delivered at the first visit, the next 2 are delivered telephonically at 1 month and 2-month time points, and the final module is delivered at home visit 2.

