4.2 SCIENTIFIC RATIONALE FOR STUDY DESIGN

Our design includes three groups:

- Control Group participants will receive an educational booklet only and will continue their usual brushing techniques (manual or electric). They will receive a smart electronic toothbrush at the end of the study (at home visit 3)
- Treatment Group 1 participants will receive an educational booklet and 2 smart electronic toothbrushes.
- Treatment Group 2 participants will receive an educational booklet, 2 smart electronic toothbrushes, and in-home and telephone coaching.

In our pilot study, both the treatment (treatment group 2) and the comparison group (treatment group 1) improved in their oral hygiene outcomes. Thus, in the present study, we have added a usual care control group to address the possibility that the smart electronic toothbrush itself may serve as an intervention ingredient.

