Clinical Oral Health Evaluation. (All groups) The hygienist performs an oral health evaluation (see detailed procedures in Section 8.1 Endpoint and other Non-Safety Assessments). The evaluation is used by the hygienist to guide tailored recommendations for the treatment plan for participants assigned to Treatment Group 2.

Assessment of technical and adaptive challenges and instruction. (Treatment Group 2) This assessment is completed in the location where the dyad normally does oral care, usually a bathroom with a large mirror over the sink. Because the interventionist and the care partner must integrate the tailored instruction, they both will observe. Standing in front of a mirror, the dental hygienist will ask the participant to brush using his/her normal toothbrush to assess the participant's toothbrushing technique and begin to identify technical challenges and areas for specific feedback on technique, including areas of the dentition missed in brushing. S/he will then demonstrate the proper technique on a mouth model using a smart electronic toothbrush. Standing in front of a mirror, participant will then be asked to brush her/his teeth again, using the smart electronic toothbrush and the technique demonstrated. This approach is based on the approach developed by others³² for the clinical setting and adapted for the in-home setting. We will recommend use of interdental cleaning aids. Using the same approach as above, the hygienist will assess interdental cleaning by participants and assess cleaning partial dentures, if applicable. The hygienist will demonstrate the correct cleaning techniques and ask the participant to return-demonstrate. The participant and care partner will then be shown how to use a disclosing tablet to identify areas of dentition missed in brushing. The care partner is given an electronic toothbrush to support the collaborative effort of the dyad in regular and appropriate oral hygiene behavior. The care partner is also asked to demonstrate use of the electronic toothbrush to ensure that s/he understands. The oral hygiene technique assessment will be conducted at each visit. Examples of technical challenges that might be identified include limited hand dexterity which will guide selection of the right tool for interdental cleaning, or gum conditions that might guide recommendations

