10.1.3 Confidentiality and privacy

Participant confidentiality and privacy is strictly held in trust by the participating investigators, their staff, the safety and oversight monitor(s), and the funding agency. This confidentiality is extended to the data being collected as part of this study. Data that could be used to identify a specific participant will be held in strict confidence within the research team. No personally-identifiable information from the study will be released to any unauthorized third party without prior written approval of the funding agency or as described in the consent form.

All research activities will be conducted in as private a setting as possible.

The study monitor, other authorized representatives of the sponsor, and representatives of the Institutional Review Board (IRB) may inspect all documents and records required to be maintained by the investigator, including but not limited to, data collected from participants and care partners as part of the study. The clinical study site will permit access to such records.

The participant's contact information will be securely stored at each clinical site for internal use during the study. At the end of the study, all records will continue to be kept in a secure location indefinitely or at least as long a period as dictated by the reviewing IRB, Institutional policies, or funding agency requirements.

Participant and care partner's research data, which is for purposes of statistical analysis and scientific reporting, will be transmitted to and stored at the NYU Data Coordinating Center for this study. This will not include the participant's contact or identifying information. Rather, participants and care partners, and their research data will be identified by a unique study identification number. The study data entry and study management systems used by clinical sites and by the NYU Data Coordinating Center research staff will be secured and password protected. At the end of the study, all study databases will be de-identified and prepared for archiving by the NYU Data Coordinating Center.

Measures Taken to Ensure Confidentiality of Data Shared per the NIH Data Sharing Policies

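### Section 8.4.3 requires notice of unanticipated problems only up to the 6-month visit, so it never covers a completed control holding the study toothbrush, nor other completers who may still be affected

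*Combined protocol and SAP*

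**What the plan says.** **The rule (8.4.3).** The section gives its reason first: "Since UPs by definition suggest that the research places participants or others at a greater risk of harm" than was known before. It then sets the scope: "all participants who are still active in the protocol (i.e. have not completed in-person 6 month study visit) will be notified in writing". These participants are also to be re-consented at their next visit.

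**When controls get the device.** Section 4.2 says of the control group: "They will receive a smart electronic toothbrush at the end of the study (at home visit 3". In the control table of section 1.3, the row "Distribution of a smart electronic toothbrush" has a single mark, at Time 7 (home visit 3, week 24).

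**Devices in the treatment groups.** Section 4.1: "Participants in Treatment Group 1 and Treatment Group 2 will receive two smart electronic toothbrushes". Section 6.1.1, for Treatment Group 2: "The care partner is given an electronic toothbrush to support the collaborative effort of the dyad".

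**Records.** Section 2.3.1 lists breach of confidentiality as a risk: "There is a small risk that unauthorized persons could get access to personal or study-related participant information". Section 10.1.3 says that after the study "all records will continue to be kept in a secure location indefinitely", or at least for the period that the IRB, the institution or the funder requires.

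**Who counts as a participant.** Section 2.2 reserves the word for the person with mild dementia. Section 10.1.1.2, on consent, uses it for both members of the dyad.

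**Other routes.** Section 8.3.7 (reporting events to participants) is marked not applicable. Section 8.4.2 sends reports to the IRB, the DSMB and NIDCR, and these must describe corrective actions taken or proposed. Section 10.1.2 has participants and care partners informed if the study is suspended or terminated.

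**The concern.** The reason given for notifying people is that they, or others, face more risk than was known. The limit placed on notification is the 6-month visit. These two do not match where exposure starts at that visit or continues past it.

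The control group shows this most plainly. The visit that puts the study toothbrush in a control participant's hands is the visit that takes that participant out of the rule. The protocol itself treats brushing with an electric toothbrush as a possible source of complications (8.3.1), and it records adverse events for 7 days, and serious ones for 30 days, after the last day of participation (8.3.4). A device event in a control could therefore be recorded and judged an unanticipated problem, while 8.4.3 would not require that this control, or any other completed control, be told.

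What is at stake is information to people with cognitive impairment and their care partners about a risk that may still apply to them. Endpoints, analysis and inference are not affected.

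**Working it through.** **Step 1. Set each group against the rule.**

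| Group | Possible exposure after the 6-month visit | Notice required by 8.4.3? |
|---|---|---|
| Completed controls | Study toothbrush, received at that visit (1.3, 4.2) | No |
| Completed Treatment Group 1 and 2 participants | Two study toothbrushes each (4.1); the documents describe no return | No |
| Completers in any group | Records kept by the sites (10.1.3) | No |
| Treatment Group 2 care partners | Toothbrush given to them (6.1.1) | Not clear at any time |
| Care partners generally | Stored study data (10.1.3) | Not clear at any time |

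The first row needs no assumption about timing or enrolment. It follows from the place of one visit in two sections.

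**Step 2. Look for another provision that closes the gap.** Section 8.3.7 is not applicable. Section 8.4.2 names recipients, but participants are not among them. Section 10.1.2 reaches participants and care partners, and is not limited to active ones, but only on suspension or termination. None of these requires notice to completers while the study runs on, or after it ends normally.

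**Step 3. Reproduce the only head count in the documents** (sample size table dated 05/08/24, ahead of the SAP's study design section).

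- Consented: 20 + 20 + 20 = 60, as stated.
- Completed: 18 (Treatment Group 1) + 17 (Treatment Group 2) + 19 (control) = 54, as stated.

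**Step 4. Count those outside the rule on that date.**

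- Not completed: 60 − 54 = 6. At most these 6 were still active; any who had withdrawn lower that number.
- Outside the rule: at least 54 of 60, and 54/60 = 90%.
- Completed controls outside: 19 of 19.

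**Step 5. Restrict to people holding a device.** Take every consented Treatment Group 1 and 2 participant as having received toothbrushes, and every completed control as having received one at home visit 3.

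- Device holders: 20 + 20 + 19 = 59.
- Still inside the rule: at most (20 − 18) + (20 − 17) = 5.
- Outside: at least 54 of 59, and 54/59 = 91.5%.

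If fewer of those 5 received toothbrushes, or some had withdrawn, the share outside is higher.

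**The case against.** The strongest reply is that 8.4.3 sets a minimum. Notice there is tied to re-consent at the next visit, which only active participants have, and nothing in the section forbids telling others. Every unanticipated problem goes to the IRB and NIDCR within 48 hours or 7 days with corrective actions (8.4.2), and contacting former participants could be one of them. This stands. A reader might infer that completers would not be told; the documents support only that the protocol does not require it.

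A second reply concerns size. The count of 05/08/24 comes late, when most of those enrolled had finished. A reader might infer that most exposed people are outside the rule at all times. That is not supported: early in enrolment most people are still active, and the documents give no enrolment curve from which to say when this changes. A breach may also touch one file or one site, so the share of everyone enrolled is not the share affected by a given breach.

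Third, a reader might take a toothbrush problem and a data breach to be the likeliest unanticipated problems. The documents do not rank them. Under 8.4.1 a problem must be unexpected in nature, severity or frequency, while breach of confidentiality is already disclosed (2.3.1) and toothbrush complications are already named (8.3.1). The study is also described as minimum risk (8.3.3.3).

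Fourth, the de-identified archive adds little to the confidentiality point: sections 10.1.3 and 10.1.4 describe coded or de-identified data without contact details. The exposure that remains lies in the records held at the sites.

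Last, the consent form and the Manual of Procedures are not part of the documents reviewed. Return of toothbrushes, or notice of a breach, may be covered there. The absence of a return procedure in the protocol and SAP does not show that none exists.

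These replies narrow the point. They do not remove the mismatch between the stated reason and the stated cut-off in the section written for this purpose.

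**Conclusion.** The point holds as a gap in a minimum rule. Section 8.4.3 requires notice only before the 6-month visit is completed, so it never reaches a completed control who has the study device. It also leaves out completed treatment-group participants and completers whose records are retained, and it is unclear about care partners.

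The structural finding on controls rests on the text alone. The size, at least 54 of 60 participants on 05/08/24 including all 19 completed controls, rests on counting all six non-completers as active, which favours the protocol, and it applies to that date. The device figure of at least 54 of 59 also assumes that toothbrushes were handed out as scheduled and that past recipients count as exposed. For the treatment groups, continuing exposure depends on the toothbrushes not being returned, which the documents leave open.

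This is a cheap improvement to participant protection. It does not bear on the validity of the trial's results.

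**What to change.** Amend 8.4.3 so that, when an unanticipated problem concerns a study-supplied toothbrush or retained identifiable records, written notice also goes to:

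- participants who have completed or withdrawn and may still be affected;
- care partners who may still be affected, named explicitly so that the meaning of participant is not in doubt.

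Keep re-consent for active participants only, since it has no purpose for those who have finished. If the consent form or Manual of Procedures already provides for such notice or for return of the toothbrushes, 8.4.3 should refer to it.

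The cost is the amendment itself, and letters or calls to former participants if such a problem arises. Sites already store participants' contact information and keep records after the study (10.1.3), and the participant lives with the care partner at entry (5.1). Because 10.1.3 describes contact information as for use during the study, the amendment should state that it may be used later for this purpose. No analysis, sample size or study procedure changes.

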9 STATISTICAL CONSIDERATIONS

9.1 STATISTICAL HYPOTHESES

Primary Efficacy Endpoint(s):

- H1 (Objective 1): There will be an improvement in the oral hygiene clinical outcomes (lower plaque index and lower gingival index) from baseline to Month 3 and Month 6, and from Month 3 to Month 6. Treatment Group 1 will have a higher rate of improvement than the control group while Treatment Group 2 will have the highest rate of improvement.
- H2b (Objective 2b): The effects of the intervention on oral hygiene clinical outcomes (i.e., plaque index and gingival index) will be mediated by a set of mediating variables controlling for selected key covariates.
- H3a (Objective 3a): The effects of the intervention on oral hygiene clinical outcomes (i.e., plaque index and gingival index) will be mediated by oral hygiene behavioral outcomes controlling for selected key covariates.
- H3b (Objective 3b): The effects of the intervention on oral hygiene clinical outcomes (i.e., plaque index and gingival index) will be mediated by care partner's factors, and then mediated by oral hygiene behavioral outcomes controlling for selected key covariates.

Secondary Efficacy Endpoint(s):

- H1 (Objective 1): There will be an improvement in the oral hygiene behaviors (better oral hygiene skills and higher frequency of toothbrushing) from baseline to Month 3 and Month 6, and from Month 3 to Month 6. Treatment Group 1 will have a higher rate of improvement than the control group while Treatment Group 2 will have the highest rate of improvement.
- H1 (Objective 1): There will be an improvement in the oral hygiene behaviors (longer duration of toothbrushing) from the first week of the intervention (average in Week 1) to Month 3 (average in Month 3) and Month 6 (average in Month 6), and from Month 3 to Month 6. Treatment Group 2 will have longer duration of toothbrushing than the Treatment Group 1.
- H2a (Objective 2a): The effects of the intervention on oral hygiene behavioral outcomes (i.e., the duration and frequency of toothbrushing and oral hygiene skills) will be mediated by a set of mediating variables controlling for selected key covariates.

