- Participant oral hygiene behavior (investigator developed) asks about the participants' frequency of toothbrushing and flossing. The response categories will be coded as 1= Twice a day or more, 2=once a day, 3= Several times a week, 4= Once or less than once a week, 5=Hardly ever, and 6= Never. This measure also includes the frequency of reminders that the care partner provides. The response categories include 1=Very often, 2=Sometimes, 3=Occasionally, and 4= Not at all
- Own oral hygiene behavior (investigator developed) asks about care partners' frequency of toothbrushing, flossing, and mouth rinse. The response categories will be coded as 1= Twice a day or more, 2=once a day, 3= Several times a week, 4= Once or less than once a week, 5=Hardly ever, and 6= Never.

Study coordinator collects data from log and a smart toothbrush

- Oral hygiene behavior data collected from log for Treatment Group 2: Duration of toothbrushing and frequency of toothbrush. Duration of brushing will be measured as a continuous variable; frequency will be coded as an ordinal variable, 1-3.
- Oral hygiene behavior data from a smart toothbrush for Treatment Group 1 and 2: Duration of toothbrushing and frequency of toothbrushing. Duration of brushing will be measured as a continuous variable; frequency will be measured as a continuous variable..

After both sets of questionnaires are completed, the dental hygienist will perform a complete oral health evaluation on the participant:

- Determination of missing teeth (Number of missing teeth coded as a continuous variable.)
- Plaque Index⁴⁴ using UNC Modified Green and Vermillion Oral Hygiene Index (1960) Plaque will be measured as 0= No plaque, 1=Plaque covers < 1/3 tooth, 2=Plaque covers >=1/3 but < 2/3 tooth, and 3=Plaque covers >=2/3 tooth.

- Gingival Index⁴⁵ using UNC Modified Loe and Silness Gingival Index. Gingival inflammation is classified as 0 = Normal gingiva, 1 = Mild inflammation, no bleeding on probing, 2 = Moderate inflammation, bleeding on probing, 3 = Severe inflammation, tendency to spontaneous bleeding.

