9.4 STATISTICAL ANALYSES

9.4.1 GENERAL APPROACH

A statistical analysis plan (SAP) will be prepared and finalized prior to database lock and unblinding of participant's treatment assignment. This document will provide further details regarding the definition of analysis variables and analysis methodology to address all study objectives. A blinded data review will be conducted prior to unblinding of the participants' treatment assignments. This review will assess the accuracy and completeness of the study database, participant evalability, and appropriateness of the planned statistical methods. The SAP will not be posted publicly or registered before the study begins.

We will conduct data analysis in the following steps:

- Descriptive analysis on the sample characteristics, potential mediators, and oral hygiene behavioral and clinical outcomes. For the categorical variables, we will present percentages. For continuous variables, we will present means (with range and standard deviations).
- We will conduct ANOVA and Chi-Square analysis to compare group differences for the variables listed above. This will be based on two-tailed hypothesis testing. We will use p-value and 95% confidence interval for statistical significance test. P value of 0.05 will be considered the level of significance.
- We will use linear mixed models for continuous outcomes (e.g., plaque index, gingival index, oral hygiene skills, and duration of toothbrushing from smart toothbrush) accounting for within-participant correlation over time.
- We will use generalized linear mixed models for ordinal variables (e.g., self-reported duration of toothbrushing) accounting for within-participant correlation over time.
- Key covariates will be specified in the SAP.
- The tests for the underlying assumptions for the models will be specified in the SAP.

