9.4.3 ANALYSIS OF THE SECONDARY ENDPOINT(S)

The secondary endpoints are oral hygiene behavioral outcomes.

We will test whether the intervention is associated with differences across groups in the oral hygiene behavioral outcomes. We will use linear mixed models for continuous and ordinal outcomes accounting for within-participant correlation over time. In addition to group, all models will be adjusted for site and time point and the interaction between group and time point – to assess whether group difference varied over time – as fixed effects – and include a random effect for participants to handle within-participant clustering. Significant interaction between group and time point ($p < 0.05$) will provide statistical evidence for the efficacy of the intervention in improving oral health outcomes in Treatment Group 2 as compared to Treatment Group1 and the Control Group. Similar to the approach taken with the primary endpoints, we will then test the strength of the indirect effects of intervention on oral hygiene behavioral outcomes through mediators.

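### Protocol 9.1 and 9.4.3 judge device-recorded brushing duration by change after Week 1, which subtracts any coaching effect Treatment Group 2 already shows in that week

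*Combined protocol and SAP*

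**What the plan says.** Protocol 9.1 lists brushing duration as a secondary efficacy hypothesis: "longer duration of toothbrushing) from the first week of the intervention (average in Week 1) to Month 3 (average in Month 3", and on to Month 6. The between-group part of that hypothesis is that TG2 brushes for longer than TG1. Brushing frequency and skill have a separate hypothesis, which starts from baseline.

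Protocol 9.4.1 gives "duration of toothbrushing from smart toothbrush" as an example of a continuous outcome for the linear mixed model. Section 8.1 limits the device record to two arms: "Oral hygiene behavior data from a smart toothbrush for Treatment Group 1 and 2". Section 9.4.3 fits group, time point, their interaction and site, and then states: "Significant interaction between group and time point ($p < 0.05$) will provide statistical evidence for the efficacy of the intervention".

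On coaching, section 4.1 says: "One module is delivered at the first visit, the next 2 are delivered telephonically at 1 month and 2-month time points". The TG2 schedule in 1.3 marks both the coaching module and tailored oral hygiene instruction at Home Visit 1. Section 6.1.1 describes that visit. The hygienist watches usual brushing and demonstrates technique, and then: "Standing in front of a mirror, participant will then be asked to brush her/his teeth again, using the smart electronic toothbrush". TG1 gets only basic instruction on using the device.

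The SAP's duration outcome is a three-level item reported by the dental hygienist. Its section on electronic toothbrush data describes an agreement analysis and no comparison between arms.

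**The concern.** A group-by-time interaction measures efficacy well when the first time point precedes treatment, because randomisation then makes the arms equal in expectation at the start. Week 1 device data do not meet that condition. By then TG2 has had Module 1, which introduces cueing and goal setting, and a tailored demonstration with the same brush. TG1 has had neither.

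Whatever TG2 gains in that first week is treated as its starting level and removed from the later differences. The decision rule therefore answers whether the gap changed after Week 1, while the hypothesis asks whether TG2 brushes for longer. TG2 against TG1 is the comparison that isolates coaching from the brush, and protocol 2.1 presents objective brushing data as a significant aspect of the study. If the device comparison were run as the protocol words it, an early and lasting coaching effect could go unrecognised.

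**Working it through.** **The plan's own figure.** The documents give no power figure for device duration. The only sample-size figure for direct group effects is in protocol 9.2: 107 participants for 80% power at effect size 0.3. It is reproduced by reading 0.3 as Cohen's f in a three-group, 2-df large-sample test: the required noncentrality is 9.635, and 9.635 / 0.3² = 107.05. This has no bearing on the Week 1 question.

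**Inputs from the documents.** Two-sided α = 0.05 (9.4.1). Target 120 over three equal arms, so 40 per arm (9.2, 6.3). Completers at 8 May 2024: 18 in TG1 and 17 in TG2 (table before the SAP text), so 18 per arm is slightly generous.

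**Assumptions, not in the documents.** TG2 minus TG1 effect d = 0.8 SD at Months 3 and 6, within-person correlation ρ = 0.5, equal variances, complete data. Ranges are given below.

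**Step 1, free of assumed values.** Let a share f of the effect be present in Week 1, so the TG2 minus TG1 differences at the three times are (f·d, d, d). The changes from Week 1 are both (1 − f)·d. If f = 1 they are d − d = 0, and the interaction test rejects at its 5% error rate whatever d, n or ρ. An independent simulation of 20,000 trials gave 5.01% at 40 per arm and 5.04% at 20.

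**Step 2, formulas.** With SD = 1 and n per arm:
- Interaction: F test on 2 and 4(n − 1) df, noncentrality λ = n·d²·(1 − f)² / [3(1 − ρ)].
- Month 3 level contrast: t test on 2n − 2 df, noncentrality d·√(n/2).

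The factor (1 − f)² gives the loss directly. Half the effect in Week 1 leaves 25% of the noncentrality, and a quarter leaves 56%.

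**Step 3, results at d = 0.8, ρ = 0.5.**

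| Share in Week 1 | λ, n = 18 | Interaction power | λ, n = 40 | Interaction power |
|---|---|---|---|---|
| All | 0 | 5% | 0 | 5% |
| Half | 1.92 | 21% | 4.27 | 43% |
| A quarter | 4.32 | 43% | 9.60 | 79% |
| None | 7.68 | 68% | 17.07 | 96% |

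The Month 3 level contrast does not depend on f. At n = 18, 0.8 × √9 = 2.40 and power is 65%. At n = 40, 0.8 × √20 = 3.58 and power is 94%.

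**Step 4, ranges.**
- Over ρ from 0.3 to 0.7 at d = 0.8, interaction power with half the effect in Week 1 is 16% to 33% (n = 18) or 32% to 65% (n = 40). With a quarter present it is 32% to 65%, or 64% to 95%. At ρ = 0.7 and a quarter present, the interaction therefore does as well as the level contrast.
- The level contrast falls to 31% or 60% at d = 0.5, and to 14% or 26% at d = 0.3.

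**The case against.** The strongest objection is that the SAP does not run this test. Protocol 9.4.1 leaves variable definitions and methods to the SAP. There, duration is hygienist-reported and device data serve an agreement analysis. That outcome also has a sound baseline: at Home Visit 1 the hygienist watches the participant brush with the usual toothbrush before demonstrating anything. A reader might infer that the trial will report a real, sustained coaching effect as null. The documents do not support that, because no device comparison between arms is currently described.

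Second, the interaction sentence in 9.4.3 is generic. It refers to all three arms, does not mention Week 1, and cannot apply unchanged to data the Control Group does not have. The model contains a group term, and 9.1 already words the level hypothesis. This stands in part: the missing step is naming the level contrast as the deciding test.

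Third, an effect complete by Week 1 is an extreme case. Communication strategies begin in Module 2, later modules come at weeks 4, 8 and 12, and 6.1.2 says three months were chosen to allow learning. With gradual build-up the interaction keeps much or all of its power, so total loss of power should not be read as the general result.

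A reader might also infer that a fading effect would count as efficacy, since the interaction test has no sign. Section 9.1 states a direction, improvement with TG2 longer, so a shrinking gap would contradict the hypothesis under test.

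What survives is that the protocol keeps the hypothesis and the criterion, and the SAP does not withdraw them.

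**Conclusion.** The point holds for the protocol's device-duration hypothesis judged by the interaction criterion. Any part of the coaching effect present in Week 1 is subtracted, and the criterion does not match the level difference stated in 9.1. The cancellation is algebraic. Its size depends on the unknown share present in Week 1 and on the assumed 0.8 SD and correlation 0.5: the loss against the level contrast runs from total, through about 44 to 51 percentage points at a half (65 − 21, 94 − 43) and 15 to 22 at a quarter (94 − 79, 65 − 43), to none if everything builds later.

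Frequency and skill, which 9.1 starts from baseline, are not affected, nor is the SAP's hygienist-reported duration. The SAP's device baseline window, six days around the baseline date, shares the limitation, since no device data before coaching are planned. It matters only if that window is used as a baseline in a comparison of arms. Practical weight is modest: a defect in a retained protocol hypothesis, with no demonstrated effect on an analysis the SAP commits to.

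**What to change.** In protocol 9.1 and 9.4.3, and in the SAP if a device comparison is to be reported, name the TG2 minus TG1 difference in the Month 3 average duration as the device-duration test, with Month 6 secondary and site as covariate. State that Week 1 is a post-treatment time point that is neither subtracted nor adjusted for, and that the interaction is not the efficacy criterion for this outcome. Randomisation makes the level contrast valid without a device baseline.

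No new data are needed. In the protocol the change is wording. In the SAP it adds one secondary comparison, on device data that the SAP expects to be missing for a substantial proportion of participants. Report it with the number contributing data in each arm, and include it in the secondary false-discovery-rate family. Power would be low for a small effect. If no device comparison is intended, the SAP should say that the protocol's device-duration hypothesis is not tested.
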